3.3 Safety and tolerability variables

Missing safety data will generally not be imputed. However, safety assessment values of the form of “< x” (i.e., below the lower limit of quantification) or > x (i.e., above the upper limit of quantification) will be imputed as “x” in the calculation of summary statistics but displayed as “< x” or “> x” in the listings. Additionally, adverse events that have missing causality (after data querying) will be assumed to be related to study drug.

Safety and tolerability will be assessed in terms of AEs, deaths, laboratory data, vital signs including blood pressure and ECGs. Refer to section 4.1 for general considerations for safety assessments. The safety analysis set will be used for all summaries.

3.3.1 Exposure and dose interruptions

Exposure will be defined as follows:

Total (or intended) exposure of study treatment

- Total (or intended) exposure = min(last dose date where dose > 0mg, date of death, date of DCO) – first dose date + 1

Actual exposure of study treatment

- Actual exposure = intended exposure – total duration of dose interruptions, where intended exposure will be calculated as above and a dose interruption is defined as any length of time where the patient has not taken any of the planned daily dose.

The actual exposure calculation makes no adjustment for any dose reductions that may have occurred. An interruption is defined to be any time a patient has not received study treatment for at least 1 day.

Missed or forgotten doses

Missed and forgotten doses should be recorded on the EX module as a dose interruption with the reason recorded as “Subject forgot to take dose”. These missed or forgotten doses will not be included as dose interruptions in the summary tables. However, these missed and forgotten doses will be considered in the derivation of actual exposure.

Patients who permanently discontinue during a dose interruption

If a patient permanently discontinues study treatment during a dose interruption, then the date of last administration of study medication recorded on DOSDISC will be used in the programming

Safety Follow-up

- Total Safety Follow-up = min((last dose date + 30 days), date of withdrawal of consent, date of death, date of DCO) – first dose date +1

3.3.2 Dose Intensity

Relative dose intensity (RDI) is the percentage of the actual dose delivered relative to the intended dose through to treatment discontinuation. Relative dose intensity (RDI) will be defined as follows:

$RDI = 100\% * d/D$, where d is the actual cumulative dose delivered up to the actual last day of dosing and D is the intended cumulative dose up to the or the actual last day of dosing. D is the total dose that would be delivered, if there were no modification to dose or schedule.

Intensity of cediranib and olaparib will summarised separately. The intended cumulative dose is defined as 200mg olaparib twice daily and 30mg cediranib once daily.

3.3.3 AEs

AEs and SAEs will be collected throughout the study, from date of first dose of either IP until 30 days after the last dose of study medication. The Medical Dictionary for Regulatory Activities (MedDRA)(using the latest MedDRA version available at database lock) will be used to code the AEs. AEs will be graded according to the National Cancer Institute Common Terminology Criteria for AEs (CTCAE Version 4.03).

If partial dates of onset occur, a conservative approach will be followed and events will be assumed to be treatment emergent unless there is convincing evidence to the contrary.

The following variables will be collected for each AE;

- AE verbatim
- The date when the AE started and stopped
- Changes in CTCAE grade will be reported for AEs of diarrhoea, fatigue, hypertension and nausea. For all other AEs, only the highest attained CTCAE grade will be reported.
- Whether the AE is serious or not
- Investigator causality assessment against each of the IP(s) (yes or no)
- Action taken with regard to each of the IP(s)
- Outcome (if resolved with sequelae then sequelae should be recorded).

In addition, the following variables will also be collected for SAEs:

- Date AE met criteria for SAE
- Date Investigator became aware of SAE
- AE seriousness criteria
- If the patient was hospitalized:
- Date of hospitalization
- Date of discharge

The following variables will also be collected for deaths:

- Probable cause of death
- Date of death
- Autopsy performed
- Causality assessment in relation to IPs and/or Study procedure(s).

Groups of preferred terms will be used to identify adverse events of special interests (AESIs); these preferred terms will be listed before database lock and documented in the Study Master File. The AESIs for cediranib will include PRES, arterial thromboembolic events, symptomatic left ventricular dysfunction and cardiac failure, nephrotic syndrome, renal thrombotic microangiopathy, liver failure, diarrhea, fatigue, hypertension and nausea. The AESIs for olaparib will include MDS/AML, new primary malignancy (other than MDS/AML) and pneumonitis.

For the purposes of this study all AESIs identified above will be reported for both IPs.

Any AE occurring before the start of IP or more than 30 days after discontinuation of IPs will be included in the data listings but will not be included in the summary tables of AEs.

Any AE occurring within 30 days of discontinuation of IPs (i.e., the last dose of cediranib+olaparib) or the last dose of the last IP to be discontinued, in the rare case where discontinuation dates are different will be included in the AE summaries. Any events in this period that occur after a patient has received further therapy for cancer (following discontinuation of cediranib+olaparib) will be flagged in the data listings.

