5.1.4 Survival assessment

Assessments for survival should be made every 8 weeks (relative to first dose) following objective disease progression or discontinuation from treatment. Survival information may be obtained via telephone contact with the patient, patient's family or by contact with the patient's current physician. OS will be analyzed at the time of the primary analysis; patients should be contacted or other data sources checked (see Section 3.10.2) in the 2 weeks following the data cut-off for the primary analysis to provide current complete survival data. Subsequent anti-cancer therapies should also be recorded.

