6.3.3 Adverse events after the 30 day follow up period

For olaparib pharmacovigilance purposes and characterization of events of special interest, any case of MDS/AML or new primary malignancy occurring after the 30 day follow up period should be reported to AstraZeneca Patient Safety whether it is considered a non-serious AE (eg, non-melanoma skin cancer) or SAE, and regardless of investigator's assessment of causality. These AEs must be reported according to the timelines for reporting an SAE (see Section 6.4). Investigators will be asked during the regular follow up for OS if the patient has developed MDS/AML or a new primary malignancy and prompted to report any such cases. A questionnaire will be sent to any investigator reporting MDS/AML, pneumonitis, or new primary malignancy as an aid to provide detailed information on the case.

At any time after a patient has completed the study, if an Investigator learns of any SAE or death, unrelated to SAEs of special interest, and he/she considers there is a reasonable possibility that the event is causally related to the IPs, the Investigator should notify AstraZeneca, Patient Safety.

Patients who are gaining clinical benefit in the opinion of the Investigator are allowed to continue IPs post FPV and all SAEs must continue to be collected and reported to Patient Safety within the usual timeframe.

Otherwise, after end of study there is no obligation to actively report information on new AEs or SAEs occurring in former study patients. This includes new AEs/SAEs in patients still being followed up for survival but who have completed the post treatment follow up period (30 days).

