- Any AE leading to dose interruption
- Any AE leading to dose reduction
- Any AE leading to dose modification (interruption and/or reduction)
- Any other significant AE (if applicable)

The number and percentage patients reporting each AE will be summarised, by SOC (sorted alphabetically) and PT (sorted by descending overall total) The following summaries will be produced:

- AEs by SOC and PT.
- AEs by maximum reported CTCAE grade, by SOC and PT.
- AEs of CTCAE grade 3 or higher, by SOC and PT.
- AEs causally related by IP, by SOC and PT.
- AEs leading to hospitalisation, by SOC and PT.
- AEs leading to dose interruption, by SOC and PT.
- AEs leading to dose reduction, by SOC and PT.
- AEs with outcome of death, by SOC and PT.
- AEs with outcome of death, causally related by IP, by SOC and PT.
- SAEs by SOC and PT.
- SAEs causally related by IP, by SOC and PT.

51(56)

- AEs leading to discontinuation of either IP (listed separately), by SOC and PT.
- OAEs by SOC and PT (if applicable).

In the above summaries, patients with more than one AE within a particular SOC are counted only once for that SOC. Similarly, patients with more than one AE within a particular PT are counted only once that PT. For summaries by maximum reported CTCAE grade with multiple AEs within a particular SOC or PT will be counted under the category of their most severe AE within that SOC or PT.

A summary of deaths will be provided, detailing deaths due to disease only, deaths where AE outcome is death only or both.

AEs of special interest

The AESIs for Cediranib are as follows: PRES, arterial thromboembolic events, and the Important Potential Risks: symptomatic left ventricular dysfunction and cardiac failure; nephrotic syndrome; renal thrombotic microangiopathy, liver failure, and (per eCRF) diarrhea, fatigue, hypertension and nausea. The AESIs for Olaparib are as follows: potential risks of MDS/AML, new primary malignancy (other than MDS/AML) and pneumonitis.

Grouped summary tables of certain MedDRA preferred terms will be produced and may also show the individual preferred terms which constitute each AESI grouping. Groupings will be based on preferred terms provided by the medical team prior to DBL, and a listing of the preferred terms in each grouping will be provided.

Summaries of the above-mentioned grouped AE categories will include number (%) of patients who have:

- At least one AESI presented by outcome

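### MDS/AML and new primary malignancies are sought beyond the 30-day safety follow-up, but on the plain reading of the SAP late cases are listed at most and not counted in the AE and AESI summary tables

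*SAP*

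**What the plan says.** **Collection.** Under Protocol 6.3.3, "any case of MDS/AML or new primary malignancy occurring after the 30 day follow up period should be reported to AstraZeneca Patient Safety", whether serious or not and whatever the investigator's view of causality. The section gives two reasons: olaparib pharmacovigilance, and characterising events of special interest. Collection is active as well as passive: "Investigators will be asked during the regular follow up for OS if the patient has developed MDS/AML or a new primary malignancy". Protocol 5.1.4 sets the rhythm of that follow-up: "Assessments for survival should be made every 8 weeks (relative to first dose) following objective disease progression or discontinuation from treatment". Protocol 3.9.1 ends survival follow-up at the data cut-off for the primary analysis.

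**Status of the events.** SAP 3.3.3 states: "The AESIs for olaparib will include MDS/AML, new primary malignancy (other than MDS/AML) and pneumonitis". It identifies AESIs through groups of AE preferred terms.

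**Tables.** The same SAP section says that AEs and SAEs are collected up to 30 days after the last dose. Its inclusion rule for the summaries begins "Any AE occurring within 30 days of discontinuation of IPs". AEs occurring "more than 30 days after discontinuation of IPs will be included in the data listings but will not be included in the summary tables". SAP 4.2.9 repeats the list ("The AESIs for Olaparib are as follows: potential risks of MDS/AML, new primary malignancy (other than MDS/AML) and pneumonitis") and describes the AESI output: "Grouped summary tables of certain MedDRA preferred terms will be produced". It states no separate time window, any-time row or late-event table for these two AESIs.

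**The concern.** The protocol treats 30 days as long enough for ordinary AEs but not for two named olaparib risks, and asks sites to keep looking for them. The SAP then applies its 30-day table rule without distinguishing those two. The late cases that the extended collection can find would therefore be missing from the reported incidence.

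The safety objective is to evaluate the safety and tolerability of the combination. Someone reading only the summary tables would see an incomplete numerator for two AESIs, with nothing to show that the study had looked for later cases.

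A second, related problem is the SAP's collection sentence. It closes AE and SAE collection at 30 days and does not acknowledge the exception in Protocol 6.3.3. The protocol routes late cases to Patient Safety, so it is unclear whether they would reach the clinical database from which the listings are drawn.

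**Working it through.** The plan states no figure on this point, so there is none to reproduce. The check is mainly a comparison of rules, with a small calculation for scale.

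**Tracing one late case.** Take a patient who stops both drugs, enters survival follow-up and is diagnosed with MDS 90 days after the last dose, before data cut-off.

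| Step | Source | Result |
|---|---|---|
| Must it be reported? | Protocol 6.3.3 | Yes, to Patient Safety |
| Will the site be asked about it? | Protocol 6.3.3, 5.1.4 | Yes, during survival follow-up |
| Is it an AESI? | SAP 3.3.3, 4.2.9 | Yes, for olaparib |
| Is it within the SAP collection period? | SAP 3.3.3 | No, that ends at 30 days |
| Is it in the listings? | SAP 3.3.3 | Yes, if it reaches the study database |
| Is it in the AE summary tables? | SAP 3.3.3 | No |
| Is it in the AESI summary tables? | SAP 3.3.3 with 4.2.9 | No, on the plain reading |

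The last row is an inference. The exclusion is worded for AE summary tables. AESIs are groups of AE terms defined in the same section, and SAP 4.2.9 gives no other window, so the rule carries over. SAP 4.2.9 does not restate it.

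SAP 3.3.1 also caps safety follow-up at last dose plus 30 days. The SAP amendment history records that post-treatment AE analysis was taken out of 4.2.9. That is background only, but it fits the absence of a late-event table in the current text.

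**Scale of one case.** Input: n = 60, the approximate planned sample size in Protocol 8.2. The number of cases x is an assumption. Intervals are Clopper-Pearson 95%: the lower limit is the 0.025 quantile of Beta(x, n − x + 1), and the upper limit is the 0.975 quantile of Beta(x + 1, n − x).

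- x = 0: 0/60 = 0%. Lower limit 0; upper limit 1 − 0.025^(1/60) = 5.96%.
- x = 1: 1/60 = 1.7%. Lower limit 1 − 0.975^(1/60) = 0.04%; upper limit from Beta(2, 59) = 8.94%.
- x = 2: 2/60 = 3.3%. Limits from Beta(2, 59) and Beta(3, 58) = 0.41% to 11.53%.

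The plan does not call for these intervals; they only show what one or two uncounted cases would do to the displayed rate.

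**The case against.** The strongest defence is that the 30-day window is a coherent on-treatment definition. Protocol 8.4.3 puts AEs within 30 days of discontinuation into the summaries, and SAP 3.3.1 defines safety follow-up over the same period, so numerator and at-risk time match. Later follow-up also includes subsequent anti-cancer therapy, which makes attribution harder. This stands as a reason to keep the window for AEs in general and to show late cases separately. It is not a reason to leave them uncounted, because the protocol names characterisation of these events as one purpose of collecting them.

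A second defence is that nothing is hidden. A reader might infer that late cases are lost. The documents do not support that:

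- SAP 3.3.3 sends them to the listings.
- Protocol 6.3.3 and 6.3.4 require targeted questionnaires.
- Protocol 9.4 provides for SAE reconciliation with the Patient Safety database.
- The summary of deaths in SAP 4.2.9 has no stated 30-day limit, so a fatal late case might appear there.

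With very few cases, a patient-level listing is informative. It still gives no incidence or denominator, and a late case appears in it only if the case is entered in the clinical database.

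A reader might also take the share of follow-up outside the window as the size of the under-count. A simulation assumed exponential times, treatment ending at progression with a median of 4 to 6 months, median OS of 12 months, uniform accrual over 12 to 24 months and cut-off 8 months after the last first dose. It puts about 25% to 46% of follow-up time beyond last dose plus 30 days. That is the time in which a solicited case would go uncounted. Without an event rate, which the documents do not give, it says nothing about how many cases would be missed.

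**Conclusion.** The point holds as a reporting gap that should be closed. The protocol deliberately extends collection for two olaparib AESIs, and the SAP's stated rule, read plainly, keeps what that extension finds out of the AE and AESI summary tables.

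Its size is modest. Case numbers are expected to be small, which is an assumption, and the primary endpoint is unaffected. In the illustration, one late case in 60 is the difference between a displayed 0% (0 to 6.0%) and 1.7% (0.04% to 8.9%). A table showing zero is a possibility, not a prediction, and cases within 30 days are tabulated as usual.

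Two stronger readings should be avoided. A reader might infer that the SAP expressly bars late cases from every AESI table; that rests on carrying the SAP 3.3.3 rule into 4.2.9, which is a strong inference but not stated text. A reader might also infer that sites are asked about these events indefinitely. The questioning is tied to survival follow-up, which ends at data cut-off; only the duty to report has no stated end, and Protocol 8.1 plans no statistical analysis after that cut-off.

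**What to change.** In SAP 3.3.3 and 4.2.9:

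1. Exempt MDS/AML and new primary malignancy from the 30-day exclusion. Keep the window for all other AEs.
2. Add a table of these two AESIs from first dose to data cut-off, split into onset within 30 days of the last dose and later onset. Flag cases arising after subsequent anti-cancer therapy, and footnote that these rows cover a longer at-risk period than other AEs.
3. Align the SAP 3.3.3 sentence on the AE collection period with Protocol 6.3.3.
4. Reconcile late cases with the Patient Safety database before lock.

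The cost is SAP wording, one extra table and a reconciliation step, plus rows whose at-risk period differs from the rest of the AE output. It should not be assumed that no further data entry is needed, because the documents do not show that late cases reported to Patient Safety are also entered in the clinical database.

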3.3.4 Clinical chemistry, haematology and urinalysis

Blood and urine samples for determination of clinical chemistry, hematology, and urinalysis will be taken at the following times:

- Hematology and Biochemistry data will be taken during screening, at day 1, weekly till week 4, every 2 weeks till week 8, and every 4 weeks from week 8 onwards. If the study treatment is discontinued then a blood sample will be taken at this time and during the day 30 follow-up visit
- A urine dipstick will be conducted during screening, at day 1, and every 4 weeks from week 8 onwards. If the study treatment is discontinued then a blood sample will be taken at this time and during the day 30 follow-up visit

Additional safety samples may be collected if clinically indicated at the discretion of the Investigator. The date, time of collection and results (values, units and reference ranges) will be recorded on the appropriate eCRF.

The clinical chemistry, hematology and urinalysis will be performed at a local laboratory at or near to the Investigator site. Sample tubes and sample sizes may vary depending on laboratory method used and routine practice at the site.

The following laboratory variables will be measured:

Table 7 Laboratory safety variables

Clinical chemistry (Serum/Plasma)	Haematology (Blood)	Urinalysis (Urine)
Albumin	Hemoglobin	Protein
Alanine Transaminase (ALT)	Platelet counts	
Aspartate Transaminase (AST)	Mean Cell Volume (MCV)	
Alkaline Phosphatase (ALP)	White Blood Cell count (WBC)	
Bilirubin, total	Absolute Neutrophil Count (ANC)	
Calcium	Absolute Lymphocyte Count	
Creatinine		
Magnesium		
Potassium		
Sodium		

All values will be classified as low (below range), normal (within range) and high (above range) based on project-specific reference ranges ([Appendix A](#)). Patient with urine protein ≥ 3.5 g/24 hours (CTCAE Grade 3 according to CTCAE v4) or urinary protein/creatinine ratio of >3.5 should be considered as nephrotic-range proteinuria.

Changes from baseline to each visit for all patients who have a baseline laboratory test and the corresponding post-baseline laboratory test will be calculated as the post-baseline test value minus the baseline test value, where baseline is the latest non-missing value collected prior to the first dose of study drug

3.3.4.1 Disease specific tumor marker samples (CA-125)

As part of the routine blood samples, all patients will have CA-125 assessment at screening, every 8 weeks on treatment, and at study discontinuation.

A rise in CA-125 alone is not sufficient to declare progression, and discontinue IPs; progression events should be determined by radiographic evidence of progression.

Retrospectively based on the data, CA-125 progression will be defined based on the Gynaecological Cancer Intergroup (GCIG) criteria, which are well-established and followed in clinical practice (Rustin et al 2011).

A patient is considered to have CA125 progression if any of the following are met:

1. Patients with elevated CA125 pre-treatment and normalisation of CA125 must show evidence of CA125 $\geq 2 \times$ upper limit of normal (ULN) on 2 occasions at least 1 week apart or
2. Patients with elevated CA125 before treatment, which never normalises, must show evidence of CA125 $\geq 2 \times$ the nadir value on 2 occasions at least 1 week apart or
3. Patients with CA125 in the reference range before treatment must show evidence of CA125 $\geq 2 \times$ ULN on 2 occasions at least 1 week apart.

3.3.5 Physical examination, height and weight

A complete physical examination as per standard clinical practice should be performed by the Investigator at baseline and every 4 weeks. If there are any clinically significant abnormal finding not related to disease progression, they should be recorded as an AE on the eCRF. Height will be assessed at screening only. Weight will be assessed at baseline, at every 4 weeks until treatment discontinuation and the 30 day safety follow-up visit.

Change from baseline weight will be calculated.

3.3.6 ECG

3.3.6.1 Resting 12-lead ECG

ECGs are required within 7 days prior to starting IPs, and when clinically indicated thereafter.

All ECGs should be assessed by the investigator as to whether they are clinically significantly abnormal / not clinically significantly abnormal. If there is a clinically significant abnormal finding at baseline, the Investigator should record this in the baseline eCRF. If there is a treatment emergent significant abnormal finding, the Investigator will record it as an AE on the eCRF.

3.3.7 Vital signs

Any clinically significant changes in vital signs (pulse rate, systolic and diastolic blood pressure, respiration rate, pulse oxygen saturation, and temperature) should be recorded as an AE.

